7.6 Criteria for Removal from Protocol Follow-Up

- a. Completion of 53 weeks on study.
- b. If a medical condition arises which in the opinion of the treating investigator precludes patient's participation in this study, the patient will then be removed from study follow-up.
- c. The patient may refuse all future follow-up data collection or contacts at any time for any reason. Follow-up through the treating investigator for hospitalizations and vital status will continue unless the patient specifically refuses to allow passive follow-up. (NOTE: The patient may refuse any follow-up data collection or contact at any time for any reason. If patient no longer wants to complete any

future study phone calls, if appropriate, the site should ask if the follow-up calls can be made solely to the patient's designated representative before removing a patient from follow-up.)

CLOSED EFFECTIVE 5/15/2020

7.7 Discontinuation of Protocol Follow-up

All reasons for discontinuation of follow-up must be documented in the **S1316 Off Protocol Notice**.

NOTE: Patients who discontinue follow-up will no longer be contacted for the scheduled telephone assessments (including contact via a designated representative), but known hospitalization data and vital status should still be reported.

7.8 Follow-Up Period

All patients will be followed until death, 53 weeks after registration, or other reason for removal from protocol follow-up per [Section 7.6](#), whichever occurs first. Patients are to remain on study follow-up even if they elect to receive follow-up care at a different institution.

8.0 TOXICITIES TO BE MONITORED AND DOSE MODIFICATIONS

8.1 NCI Common Terminology Criteria for Adverse Events

Two different versions of the NCI Common Terminology Criteria for Adverse Events (CTCAE) will be used on this study.

a. Serious Adverse Event (SAE) reporting

The CTCAE (NCI Common Terminology Criteria for Adverse Events) Version 5.0 will be utilized **for SAE reporting only**. The CTCAE Version 5.0 can be downloaded from the CTEP home page (<https://ctep.cancer.gov>) All appropriate treatment areas should have access to a copy of the CTCAE Version 5.0.

b. Routine toxicity reporting

This study will utilize the CTCAE Version 4.0 for routine toxicity reporting. A copy of the CTCAE Version 4.0 can be downloaded from the CTEP home page (<https://ctep.cancer.gov>). All appropriate treatment areas should have access to a copy of the CTCAE Version 4.0.

9.0 STUDY CALENDAR

REQUIRED STUDIES	Hospital Admission/ Baseline	W	W	W	W	W	W	W	W	W	W	W	W	W	F/U every 4 Weeks through Wk 53
		1	2	3	4	5	6	7	8	9	10	11	12	13	
PHYSICAL															
History and Physical Exam π		X													
Weight and Performance Status		X													
Patient Assessment α			X	X	X	X	X	X	X	X	X	X	X	X	
LABORATORY															
Serum Albumin		X													
CBC \dagger		X													
Electrolyte Panel (sodium, potassium, bicarbonate, chloride, BUN, creatinine) \dagger		X													
SCANS															
CT or MRI for disease assessment		X													
X-ray/Abdominal Plain Film Ω		X													
PATIENT QUESTIONNAIRES & FOLLOW-UP															
S1316 Cover Sheet for Patient-Completed Questionnaires		X	X	X	X	X	X	X	X	X	X	X	X	X	X
S1316 MDASI-GI		X	X	X	X	X	X	X	X	X	X	X	X	X	X
S1316 EQ-D5		X		X		X			X			X			
S1316 MBO Assessment			X	X	X	X	X	X	X	X	X	X	X	X	
S1316 MBO Follow-Up															X
S1316 Hospitalization Days Record β															X
S1316 Dietary Recall Contact Information Form		X													
Dietary Recall δ			X			X			X			X		X	X
TREATMENT															
Surgery (Arms 1 and 3)			X												
Non-surgical management (Arms 2 and 4)			X												

Footnotes:

α Weekly follow-up during Weeks 2-13 will take place by phone or in person if patient is in the hospital (see [Section 7.5b](#)).

β Assessment done weekly; data reported at Week 13.

\dagger Recommended laboratory values to be collected on the **S1316** On Study Form if testing is performed.

δ To be administered monthly by phone by the Arizona Diet, Behavior and Quality of Life Assessment Lab (see [Section 7.4](#)).

π Including pathology report of primary intra-abdominal cancer (see [Section 14.4b](#)).

Ω If CT is obtained for MBO confirmation, then it may be used rather than x-ray.

10.0 CRITERIA FOR EVALUATION AND ENDPOINT ANALYSIS

10.1 Primary Endpoint

The primary endpoint for this study is number of days alive and outside the hospital within the first 91 days after enrollment, as recorded on the **S1316** Hospitalization Days Record. The time window for each weekly assessment is +/- 2 days to allow for practical CRA/patient considerations including (but not limited to) scheduling of telephone calls and possible missed telephone calls.

10.2 MDASI-GI

The MDASI-GI is a well-validated instrument with each item, based on a 0-10 scale, designed as an independent domain related to specific HRQOL issues for patients with gastrointestinal cancers. While the MDASI is not intended to produce a total score, one can calculate a total symptom index. It is a valid, reliable, and concise tool to measure the severity of symptoms for patients with GI cancer. This will give the ability to compare outcomes for many of the most important patient reported outcomes for MBO patients, such as nausea, vomiting, feeling bloated, and pain. A movement of two points on each 0-10 point scale is considered as clinically meaningful and cutoff scores for indication of clinical deficits have been defined by the tool authors.

10.3 EQ-5D-5L

The EQ-5D-5L is designed for the collection of health state values using a visual analogue scale with the end points labeled best imaginable health state at the top and worst imaginable health state at the bottom having numeric values of 100 and 0 respectively. The EQ-5D-5L has been widely used in clinical trials in quality-adjusted survival efforts. (26,27,28,29) We will combine the MDASI-GI index score with EQ-5D-5L total score to produce a quality-adjusted life years (QALY)- adjusted outcome measure. (30)

10.4 Performance Status

Patients will be graded according to the Zubrod Performance Status Scale.

POINT	DESCRIPTION
0	Fully active, able to carry on all pre-disease performance without restriction.
1	Restricted in physically strenuous activity but ambulatory and able to carry out work of a light or sedentary nature, e.g., light housework, office work.
2	Ambulatory and capable of self-care but unable to carry out any work activities; up and about more than 50% of waking hours.
3	Capable of limited self-care, confined to bed or chair more than 50% of waking hours.
4	Completely disabled; cannot carry on any self-care; totally confined to bed or chair.

11.0 STATISTICAL CONSIDERATIONS

11.1 Design overview

This study is a hybrid design, incorporating both a randomized and a non-randomized component. Eligibility is defined identically in both components with the exception that patients in the randomized component will consent to randomization to either surgical management or non-surgical management (best supportive non-surgical palliative care) of their MBO in a 1:1 ratio. Randomization will determine their initial care, although the treating physician will take changes in their clinical course or other circumstances into account in determining their ongoing care plan. Patients who are medically eligible for the randomized trial but who do not consent to randomization will be offered registration into the non-randomized component. Their initial care plan (surgical versus non-surgical), as determined by the patient and his/her treating physician at the time of registration will be documented and considered their initial care plan for the analyses. If the treating team finds that an operation is required (e.g., for acute abdomen), or they would not offer the patient an operation (e.g., patient is too weak to tolerate surgery), then there is no equipoise and patient will not be accrued to the study.

The advantages of this hybrid design are that it uses the strengths of both the RCT to give an unbiased estimate of treatment differences while allowing us to accrue a larger and likely broader range of MBO patients who are eligible for surgery but unwilling to be randomized. By allowing more patients to participate while maintaining greater control of their care, we hope to improve power and potentially expand the inference to a more clinically relevant population who are treated according to usual practice patterns. These results may have higher external validity than a stand-alone through their inclusion of broader and more generalizable patient and physician populations. (31,32)

11.2 Primary Endpoint

The primary endpoint for this study is number of days alive and outside the hospital within the first 91 days after enrollment. Patients will be assessed for number of days admitted to the hospital every 7 days for 91 days.

11.3 Primary analyses

All eligible patients will be included in the analysis using the general modeling strategy pioneered by Prentice et al. for pooling data from a randomized trial and parallel non-randomized component. (33,34,35,36,37) For randomized patients, the analysis will be based on their assigned treatment according to the intent to treat (ITT) principle. For the non-randomized component, a pseudo-ITT approach will be used where patients will be included in the treatment group identified at enrollment as their initially chosen care plan (surgical versus non-surgical), as documented at registration. The primary analysis will pool data from both components using a multivariate linear regression model (after possible rescaling, if necessary to improve the distribution assumptions), including a parameter for study component. Factors considered likely to confound the association of treatment and outcome in the non-randomized component will be carefully modeled in the regression. Potential residual bias in the treatment group comparison from the non-randomized component will be assessed by estimating the interaction term between treatment group and study component (randomized vs. non-randomized). If, after adjustment for covariates, there is no evidence of substantial bias, the main treatment effect parameter in the reduced model (without the interaction term) will serve as the

basis for inference. If there is evidence of significant bias in the non-randomized component relative to the randomized component, the estimates from both the randomized and non-randomized components will be reported but the primary analysis will be based on the randomized component alone.

If the approach of Prentice et al., proves unwieldy because the number of covariates required to adjust for imbalance in the non-randomized component is too large for the sample size available, we will pursue the use of propensity scores. (38,39,40,41,42,43) In this approach, a logistic regression model would be developed in non-randomized component data to estimate the probability of selecting surgery using the baseline covariate data, both from patients and providers. The propensity score for each patient is then simply the estimated probability; this score can be used in the regression model instead of adjusting for individual confounders.

Missing data is a problem best handled by reducing it as much as possible. We have defined the primary endpoint in a way that should avoid most problems for this measure. By counting “good days” as days alive and not in the hospital, and having the CRAs maintain frequent (weekly) telephone contact with patients and their families, we expect that missingness on the primary outcome variable will be minimized. We anticipate that patients re-admitted to the hospital will generally return to the same institution as where they were enrolled, but if not, the weekly site calls will collect hospitalization and other relevant data. For other elements, we will attempt to limit the extent of missing data by assuring that only those data necessary for the study are collected, by developing database reports and triggers to monitor the completeness of data and alert CRAs to missing values, and by providing feedback to sites with higher than desirable frequencies of missing data.

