11.4 Secondary analyses

A strategy similar to that used for the primary endpoint will be employed for secondary endpoints. For other HR-QOL type endpoints (e.g., ability to eat, days of nasogastric tube, intravenous hydration, solid food, etc.) we will examine the distribution properties of these variables and determine whether a normal approximation is adequate, or whether a transformation would be required or another generalized linear model would be preferable. For failure time endpoints, such as overall survival, the analyses will be based on a Cox regression model where we will have the option of stratifying on study component and selected other key covariates rather than modeling them in the regression. QALY-adjusted analyses will incorporate the EQ-5D-5L, as described in Cheville et.al. (44)

Specific to dietary outcomes we will describe total self-reported energy intake, macronutrient intake in patients with MBO and relation to time since MBO and if this differs for those undergoing surgery versus no surgery. Similarly we will evaluate the same associations with the dietary exposure of interest being frequency of meals and alternately composition of meals (liquids, solids, mixed, feeding formulas [oral or enteral]).

Adherence adjusted analyses: Although the primary analysis will be based on the intent to treat (ITT) principle, if a substantial fraction ($> 30\%$) do not receive the initially assigned/chosen treatment, we will conduct a sensitivity analysis that takes into account the patient's received treatment through inverse probability weighting.

In exploratory analyses we will examine the extent to which we can identify subgroups of patients for whom differences in treatment effects may differ from the overall result, i.e.,

are there subgroups of individuals for whom surgery is particularly beneficial or particularly contra-indicated? To address this question, the final model for the primary analyses in the pooled data will be expanded using interaction terms between selected baseline factors and treatment assignment.

Sample sizes permitting, those of particular interest will be analyzed based on the following hypotheses:

1. Patients with ascites who undergo a surgical procedure will have poorer outcomes than those who are treated by non-surgical management.
2. Patients who have albumin < 3.0 who undergo a surgical procedure will have poorer outcomes than those who are treated by non-surgical management.

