11.5 Sample size

Our goal is to randomize at least 50 eligible patients, in equal proportions, to surgical or non-surgical care and register 130 eligible patients to the non-randomized component. Available data from 144 patients for whom number of good days could be determined show the mean number of good days of 33 with standard deviation of 25. With a total of 180 eligible patients with equal numbers in each treatment group, we would have 90% power to detect a 14-day difference in the mean number of good days using a two-sided, 0.05-level t-test. We have increased the overall target sample size to 200 to allow for potential losses to follow-up and incomplete data, for potential inefficiencies associated with imbalance in the number treated in each group in the non-randomized component and for the need to adjust for differences in baseline characteristics. For an analysis restricted to the trial alone with 50 patients randomized, the power would be .51. While this is a low power for a trial, we know that fear of randomization represents the dominant reason patients give for refusing to participate in clinical trials so to help assure adequate accrual, the sample size of the randomized component is small. (45)

Updated sample size: In October 2017, the DSMC recommended that “after the cohort accrual goal is reached, the randomization portion of the trial may continue for a probationary six-month period. The DSMC would then carefully evaluate the feasibility of randomizing patients to this trial and evaluate the ability achieve the objectives of the trial.” This recommendation followed the observation that accrual to the randomized arms has been considerably slower than expected. Accrual to the two treatment arms in the non-randomized cohort was also found to be unbalanced, favoring the non-surgical arm by more than 2:1. In accordance with the monitoring plan, the sample size targets are hereby adjusted to reflect the DSMC’s recommendations. Accrual to the non-randomized arms will continue until 166 patients have been registered in the non-randomized arms, with specific efforts to increase enrollment in the surgical choice arm. After the non-randomized arms are closed, the study will continue to accrue patients to

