the randomized component during the subsequent six months. At that time, the DSMC will evaluate the feasibility of continuing to full accrual is reached (200 patients total). June 2019 update: With the closure of the non-randomized component (with 165 of the targeted 166 patients) and the recent success in accruing patients to the randomized component (with 34 now randomized), the study has demonstrated the feasibility of meeting the original randomization goal. The study investigators have requested and the NCI has approved an increase in total accrual to 220, which would allow the randomized component to reach the initial target of 50 eligible patients randomized, consistent with the design as originally conceived.

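### Section 11.3 lets the estimated treatment-by-component interaction choose the primary estimate, with no numeric criterion and no allowance for the choice, so type I error exceeds 5% even when the non-randomized component is unbiased

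*Combined protocol and SAP*

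**What the plan says.** The primary analysis (section 11.3) is a linear regression on both components, adjusted for likely confounders, with propensity scores as a fallback. Residual bias in the non-randomized comparison is assessed by the interaction between treatment and component. Two sentences then select the primary estimate:

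- Pool: "If, after adjustment for covariates, there is no evidence of substantial bias, the main treatment effect parameter in the reduced model" (without the interaction) is the basis for inference.
- Switch: "If there is evidence of significant bias in the non-randomized component relative to the randomized component", then "the estimates from both the randomized and non-randomized components will be reported but the primary analysis will be based on the randomized component alone".

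The first condition speaks of *substantial* bias and the second of *significant* bias. Neither word is given a number. Section 11.3 states no final significance level. The only one in the documents is in the sample-size calculation in section 11.5, "using a two-sided, 0.05-level t-test". The same section says of the fallback: "For an analysis restricted to the trial alone with 50 patients randomized, the power would be .51".

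Section 11.5 also reports that the non-randomized component was unbalanced, "favoring the non-surgical arm by more than 2:1", and closed "with 165 of the targeted 166 patients". Section 11.4 adds: "A strategy similar to that used for the primary endpoint will be employed for secondary endpoints".

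**The concern.** The interaction is computed from the outcomes that are then tested. When it is large by chance, the randomized estimate has been selected for lying far from the non-randomized one, and it is more often extreme than an unselected estimate. A nominal 5% test after that selection does not give 5% overall. The undefined criterion also means that a reader cannot tell from the plan which analysis would be primary.

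The stakes are practical. With 50 randomized and 165 non-randomized patients (2:1, before adjustment), an interaction estimate between about 10.5 and 16 days would be flagged at an assumed level of 0.20 but not at 0.05. That zone holds 0.20 - 0.05 = 15% of zero-bias trials. There, the unstated threshold alone decides between a 95% interval of about +/-7 days (pooled) and about +/-14 days (randomized only).

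**Working it through.** **Inputs.** Section 11.5 gives SD 25, a 14-day target difference, 50 randomized in equal proportions (25/25) and 130 non-randomized. The June 2019 update gives 165 non-randomized. I take 130 as 65/65 and 165 at 2:1 as 55/110. The interaction level is an assumption, because the documents give none. The main calculation is unadjusted, with normal outcomes and equal variances.

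**The plan's own figures.** For 25 per arm, SE = 25 x sqrt(2/25) = 7.07 and 14/7.07 = 1.98, so power is about Phi(1.98 - 1.96) = 0.51, as stated. For 90 per arm, SE = 25 x sqrt(2/90) = 3.73 and power is about Phi(3.76 - 1.96) = 0.96. The stated 90% therefore does not follow from these inputs. That is a separate matter: neither power figure enters the type I error calculation.

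**Standard errors (days).**
- Randomized: SE_r = 7.07.
- Non-randomized: SE_o = 25 x sqrt(1/55 + 1/110) = 4.13 (65/65: 4.39).
- Interaction: sqrt(SE_r^2 + SE_o^2) = 8.19 (8.32).
- Pooled: SE_r x SE_o / SE_int = 3.57 (3.73).

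**Type I error at zero bias.** With interaction level g, the pooled estimate is independent of the interaction, so the unflagged branch contributes (1 - g) x 0.05. The flagged branch contributes P(flagged and randomized-only test significant). This is a bivariate normal probability in which the absolute correlation is SE_r/SE_int = 0.86 (0.85). For 50+165 at g = 0.05: 0.95 x 0.05 + 0.0264 = 0.0739.

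| Assumed g | 50+130 (65/65) | 50+165 (55/110) | Rejection of a true null once flagged |
|---|---|---|---|
| 0.01 | 5.8% | 5.8% | |
| 0.05 | 7.29% | 7.39% | 51-53% |
| 0.10 | 8.06% | 8.18% | 36-37% |
| 0.20 | 8.42% | 8.51% | 22-23% |
| 0.50 | 7.44% | 7.46% | |

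The SD cancels from these figures. A simulation of 1,000,000 trials with t-tests gave 7.25-7.44%, 7.99-8.22% and 8.38-8.54% at 0.05, 0.10 and 0.20. The pooled branch keeps 5%, so all the excess is in the flagged branch. At g = 0.05 only 5% of zero-bias trials are flagged. About half of those reject, and the net excess is 7.39 - 5 = about 2.4 points.

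**Covariate adjustment.** Confounders are correlated with treatment in the non-randomized component, so adjusting for them inflates SE_o and lowers the correlation. If that component's variance is multiplied by 1.5 to 2 (assumed), the same formula gives 6.7-7.0%, 7.3-7.8% and 7.7-8.2%, and flagged-branch rejection at g = 0.05 falls to 38-46%. Simulated adjusted models (R-squared 0.30 and selection strengths assumed) gave 6.8-7.2%, 7.4-8.0% and 7.9-8.3% with an adjusted randomized-only fallback. With an unadjusted fallback they gave 6.4-6.6%, 6.9-7.2% and 7.4-7.6%.

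**Power to flag a 14-day bias, unadjusted.** At g = 0.05 with 50+165: 14/8.19 = 1.71 and Phi(1.71 - 1.96) = 0.40 (50+130: 0.39). At g = 0.10 and 0.20 the figures are 52-53% and 66-67%.

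**Type I error at an assumed bias, unadjusted** (the documents give no bias):

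| Bias | Always pool | Rule at g = 0.05 / 0.10 / 0.20 | Randomized only |
|---|---|---|---|
| 7 days | 27-31% | 26-29 / 24-27 / 21-24% | 5% |
| 14 days | 77-83% | 50-52 / 40-42 / 29-30% | 5% |

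**Final level giving 5% overall at zero bias, unadjusted.** About 0.032, 0.029 and 0.029 for g = 0.05, 0.10 and 0.20.

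**The case against.** The best defence is that the rule exists to limit bias, and it does: at a 14-day bias it gives 29-52% error against 77-83% for always pooling. Eligibility is identical in the two components, equipoise is required, and covariate or propensity adjustment comes before the choice. All of that stands, but none of it removes inflation that is present at exactly zero bias.

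A second objection is that the analysis is adjusted and the final arm sizes are not fixed. The 165 are registered rather than eligible patients, Arm 4 closed early (section 7.1), and 34 patients had been randomized at the June 2019 update (34+165 at 2:1 would give 7.7%, 8.5% and 8.7%). This also stands. A reader might take the unadjusted figures as exact for this trial, or suppose that adjustment leaves them unchanged. The documents support neither, because they do not give the covariates, their strength, or whether the randomized-only fallback is adjusted.

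Third, the flagged-branch figure of about one half could be misread as the overall error rate. It applies to the 5% of zero-bias trials that are flagged at a 0.05 criterion.

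Fourth, the cited pooling method may contain a criterion. That cannot be checked here, and the plan should state its own.

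Finally, section 11.3 promises the component estimates when bias is flagged but does not bar them otherwise. A reader should not infer that they would be withheld, only that they are not promised.

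**Conclusion.** The point holds. A stated decision rule for the sole primary inference has no defined criterion. Read at a final two-sided 0.05, it does not hold 5% at zero bias for any interaction level tried from 0.01 to 0.50. For levels of 0.05 to 0.20 at the documented sizes, type I error is about 7.3-8.5% unadjusted and roughly 6.4-8.3% adjusted. The adjusted range rests on assumed covariate strength, assumed selection into treatment and the form of the fallback.

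A non-significant interaction is weak support for pooling, since before adjustment a bias as large as the target effect is missed about 60% of the time at a 0.05 criterion.

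Two stronger readings fail. The rule is not worse than always pooling when bias is large. And calibrating the final level does not make the analysis safe against real bias: at a calibrated level of about 0.032 with a 0.05 criterion, error is still 20-23% at a 7-day bias and 45-49% at 14 days (unadjusted).

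**What to change.** In section 11.3:

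1. Replace the two undefined words with one numeric interaction criterion, fixed before outcome data are seen. State whether the randomized-only fallback is covariate-adjusted.
2. Choose one of two routes.
   - Name one estimate as primary in advance. Pooled holds 5% only at zero bias. Randomized-only holds 5% whatever the bias in the other component, with the plan's stated power of .51.
   - Keep the two-step rule and state its simulated type I error and coverage, for the actual arm sizes and adjusted model, at zero bias and at several assumed biases (for example 5, 7, 10 and 14 days). If 5% at zero bias is wanted, use a final level, with matching interval, calibrated by that simulation (about 0.03 in the unadjusted illustration). Say that this does not protect against real bias.
3. In either branch, report the pooled, randomized-only, non-randomized and interaction estimates with 95% confidence intervals.

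For the exploratory endpoints in section 11.4, use the same pre-stated criterion and report all component estimates. Do not carry over the calibrated level: those endpoints have no stated error control, and survival uses a different model.

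The cost is wording, one simulation table and a few more reported estimates. With calibration at a 0.05 criterion, unadjusted power for a 14-day difference at zero bias falls from 95.2% to 93.9% (50+165) or from 94.1% to 92.5% (50+130). At 50+165 the interval half-width grows from 7.0 to 7.7 days (pooled) or from 13.9 to 15.2 days (randomized only). Without calibration, the cost is a less favourable stated error rate.
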